4.10 MISSING DATA

All data collected under this study protocol will be included in the assessment of subject safety. Missing or incomplete AE data will assume greatest relationship to study drug and/or severity.

For the primary effectiveness endpoints (WOMAC A, WOMAC C, and PGA), missing Week 12 values will be imputed when the ITT analysis population is used. The Worst Observation Carried Forward (WOCF) will be selected as the primary method of imputing missing 12 Week data. Alternate imputation methods employed will include multiple imputations (SAS PROC MI and SAS PROC MIANALYZE) and Last Observation Carried Forward (LOCF). These sensitivity analyses will be conducted for the primary effectiveness endpoint, to ensure that the primary method of imputation chosen is robust with respect to imputation method

4.11 Detection of Bias

Any breaking of the blind for individual subjects prior to formal unblinding will be documented in the clinical study report. Reason for unblinding will also be documented. Data collected after unblinding will be noted.

4.12 Outliers

No formal outlier tests are planned. Values that are outside the pre-defined range, such as a WOMAC score not between zero and four, or a PGA score not between one and five, would be queried and excluded if necessary prior to database lock.

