6.1.2 Patient’s Global Assessment of Disease Severity (PGA)

The PGA should be completed by subjects at Screening, pre-dose and pre-aspiration as applicable on Day 0 (prior to injection), and at Weeks 2, 6, 10 and 12.

Subjects are asked the following question: “Considering all the ways in which your arthritis affects you, please indicate how you are doing.”

Subjects respond by using a 5-point adjectival Likert score (0 = very well, 1 = well, 2 = fair, 3 = poor, 4 = very poor).

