11.7 COLLECTION, MONITORING AND AUDITING STUDY DOCUMENTATION, AND DATA STORAGE

11.7.1 Collection of Data and Monitoring Procedures

This study will use a 21 CFR Part 11 compliant electronic data capture system (eDC). An electronic case report form (eCRF) is used for data recording. All data requested on the eCRF must be entered and all missing data must be accounted for.

The data will be checked for completeness and correctness as it is entered by the real-time online checks applied by the eDC system. Off-line checks will also be run to perform any additional data review required. Discrepancy reports will be generated accordingly and transferred to the study center for resolution by the investigator or his/her designee.

Accurate and reliable data collection will be assured by verification and cross-check of the eCRF against the investigator's records by the study monitor (source document verification), and the maintenance of a study drug-dispensing log by the investigator.

Before study initiation, at a site initiation visit or at an investigator's meeting, a Sponsor representative will review the protocol and case report forms with the investigators and their staff. During the study a monitor will visit the site regularly to check the completeness of subject records, the accuracy of entries on the case report forms, the adherence to the protocol and to Good Clinical Practice and the progress of enrollment. The monitor will ensure during on-site visits that study medication is being stored, dispensed and accounted for according to specifications. Key trial personnel must be available to assist the monitors during these visits.

The investigator must give the monitor access to relevant hospital or clinical records, to confirm their consistency with the case report form entries. No information in these records about the identity of the subjects will leave the study center. Monitoring standards require full verification for the presence of informed consent, adherence to the inclusion/exclusion criteria, documentation of SAEs and the recording of primary efficacy and safety variables. Additional checks of the consistency of the source data with the eCRFs are performed according to the study-specific monitoring plan.

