4.4 Definition of Study Visits

This clinical trial has a total of 7 study visits during the 12-week study (see Table 6.2). The time on study for each subject observation will be defined relative to Day 0/Baseline, the day of the initial dose. For analysis, the Baseline measure is the latest measure prior to initiation of treatment.

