For any variable, unless otherwise defined, Baseline is the last assessment taken prior to the first study drug administration.

Change from Baseline:

The arithmetic difference between a post-Baseline value and the Baseline value:

Change from Baseline = (Post-Baseline Value – Baseline Value)

Percentage Change from Baseline = [(Post-baseline Value – Baseline Value) / Baseline Value] x 100

End of Study

End of study is at Visit 9 (day 84 ± 7 days), unless terminated early.

Enrollment date

Enrollment date is the same as the randomization date and is designated Day 0.

Study drug

Study drug in this study is Ampion or saline.

Randomization date

Randomization date is the day the subject is assigned a randomization number on study Day 0.

Study Day 0

Day 0 is defined as the first day that study drug is administered to the subject.

Study Day

Day of treatment: study day = (visit date - date of Study Day 0)

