| 14.2.1.20 | Summary of PGA percent change |
| 14.2.1.21 | Summary of WOMAC mean change |
| 14.2.1.22 | Summary of WOMAC percent change |
| 14.3 Safety | |
| 14.3.1 | Overall Summary of TEAEs (Analysis Population: Safety) |
| 14.3.2 | Incidence of TEAEs by System Organ Class and Preferred Term (Analysis Population: Safety) |
| 14.3.3 | Incidence of Treatment Emergent Related AEs by System Organ Class and Preferred Term |
| 14.3.4 | Incidence of Treatment Emergent Serious AEs by System Organ Class and Preferred Term |
| 14.3.5 | Incidence of TEAEs by Preferred Term in Descending Order of Frequency |
| 14.3.6 | Incidence of Treatment Emergent Related AEs by Preferred Term in Descending Order of Frequency |
| 14.3.7 | Summary of Lab Value and Change from Baseline |
| 14.3.8 | Shifts in Reference Range |
| 14.3.9.1 | Summary of Vital Signs and Change from Baseline: Pulse (bpm) |
| 14.3.9.2 | Summary of Vital Signs and Change from Baseline: Temperature (°F) |
| 14.3.9.3 | Summary of Vital Signs and Change from Baseline: Systolic Blood Pressure (mmHG) |
| 14.3.9.4 | Summary of Vital Signs and Change from Baseline: Diastolic Blood Pressure (mmHG) |
| 14.3.10.1 | Concomitant Medication Use by ATC Level 1 and WHO Preferred Term |
| 14.3.10.2 | Medication started on study by ATC Level 1 and WHO Preferred Term |

| Number | Title |
|---------------------|---|
| 14.3.10.3 | Concomitant Medication Use by WHO Preferred Term in Descending Order of Use |
| 14.3.10.4 | Concomitant Medication Use by WHO Preferred Term in Descending Order of Use for Historic Control |
| 14.3.10.5 | Medication Started on Study by WHO Preferred Term in Descending Order of Use |
| 16- Listings | |
| 16.1 | Randomization List |
| 16.2 | Inclusion/Exclusion Criteria |
| 16.3 | Protocol Deviations |
| 16.4 | Early Terminations (Include date of ET and reason for ET) |
| 16.5 | Exclusions from PP |
| 16.6 | Demographics and Baseline Characteristics |
| 16.7 | Demographics and Baseline Characteristics for Historic Control |
| 16.8 | Medical History |
| 16.9 | Concomitant Medications |
| 16.10 | WOMAC/PGA/OMERACT OARSI Responder Status |
| 16.11 | Analgesic Used within 24 hours of visit |
| 16.12 | Adverse Events |
| 16.13 | Serious Adverse Events |
| 16.14 | Laboratory Values |
| 16.15 | Physical Exam (weight (lbs), Height, any abnormality (if listed)) and Vital Signs (BP, Temp, Pulse) |
| 16.16 | X-ray Data (and abnormalities, if listed) |

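### SAP 4.12 checks PGA against a one-to-five range, but the protocol scores PGA 0 to 4 and no recode is stated, so a valid best score of 0 is queried

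*SAP*

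**What the plan says.** Protocol 6.1.2 defines the PGA as a five-category item coded "0 = very well, 1 = well, 2 = fair, 3 = poor, 4 = very poor". SAP 4.12 plans no formal outlier tests but says what happens to values outside a pre-defined range. It gives two examples. The first is WOMAC, with a range of zero to four, which agrees with Protocol 6.1.1. The second is PGA: "or a PGA score not between one and five, would be queried and excluded if necessary prior to database lock". Neither the protocol nor the SAP mentions a one-to-five version of the PGA or a conversion from 0-4.

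Three other provisions determine what follows:

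- **Response rule (SAP 3.1 and 3.2).** A PGA response needs an improvement of at least 20% over baseline and an absolute change of 0.5 point. It is one of three domains in the primary responder definition and, on its own, the second secondary endpoint.
- **Percent change (SAP 5.2 and 7).** The formula divides by the baseline value. Table 14.2.1.20 is planned as "Summary of PGA percent change".
- **Missing data (SAP 4.10).** "The Worst Observation Carried Forward (WOCF) will be selected as the primary method of imputing missing 12 Week data".

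**The concern.** A data check should accept exactly the codes that the instrument can produce. This one is shifted by one unit, and the code it wrongly catches is the best possible outcome. The rule also allows exclusion as well as a query, and it acts before database lock.

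PGA is not a minor variable here. It contributes to the primary endpoint, and SAP 4.2 tests the endpoints in a fixed order, so the PGA test must succeed before the comparison with historic saline is reached. Because percent change depends on where the scale starts, the documents also leave two possible sets of numbers for one planned table. SAP 4.13 calls for independent programming, and two programmers could each choose a different coding in good faith.

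**Working it through.** **Inputs.** Protocol PGA codes: 0, 1, 2, 3, 4 (Protocol 6.1.2). SAP accepted range: 1 to 5 (SAP 4.12). Response: improvement of at least 20% and at least 0.5 point (SAP 3.2). Percent change: (post − baseline) / baseline × 100 (SAP 5.2); improvements are shown below as positive numbers.

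**Step 1. Does the SAP range reproduce from the protocol's scale?** No.

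- Valid protocol codes outside 1 to 5: {0}.
- Codes inside 1 to 5 that the protocol does not define: {5}.
- With the range set to 0 to 4, no valid code is flagged and 5 is flagged.

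**Step 2. Does the coding alone change PGA response?** Let b be the baseline and p the Week 12 score, both on 0-4. The improvement is (b − p)/b on 0-4 and (b − p)/(b + 1) on 1-5, because the shift cancels in the numerator only.

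| b to p | 0-4 coding | 1-5 coding |
|---|---|---|
| 1 to 0 | 100% | 50% |
| 2 to 1 | 50% | 33.3% |
| 2 to 0 | 100% | 66.7% |
| 3 to 2 | 33.3% | 25% |
| 3 to 1 | 66.7% | 50% |
| 3 to 0 | 100% | 75% |
| 4 to 3 | 25% | 20% |
| 4 to 2 | 50% | 40% |
| 4 to 1 | 75% | 60% |
| 4 to 0 | 100% | 80% |

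These are the 10 improving pairs. Each is at least one point and at least 20% on both codings; the tightest, 4 to 3 on 1-5, is 1/5 = exactly 20%. The other 25 − 10 = 15 pairs show no improvement and are non-responses on both, with a baseline of 0 counted as non-response. Status therefore differs in 0 of 25 pairs. Of the 10 responding pairs, 4 end on the flagged code 0.

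**Step 3. Does the coding change Table 14.2.1.20?** Yes. With baseline 1 to 4 there are 4 × 4 = 16 non-zero changes, counting worsening as well as improvement. All 16 give different percentages, because the denominator is b on one coding and b + 1 on the other.

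**Step 4. What if a Week 12 zero were excluded?** The SAP does not say that an excluded value becomes missing; assume that it does. WOCF then replaces 0 with an earlier score that cannot be better than 0, so the PGA response stays the same or is lost. As an invented illustration, a patient with 3 at baseline, 3 at Week 2 and a removed 0 at Week 12 is assigned 3 and becomes a non-responder.

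**Step 5. Where would that reach?** The second secondary endpoint is affected directly. For the primary endpoint, take a patient who misses the 50%/1-point criterion for pain and for function:

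- both 20% pain and function criteria met: responder whatever the PGA;
- neither met: non-responder whatever the PGA;
- exactly one met: the PGA decides.

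Only the last group can change status on the primary endpoint.

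**The case against.** The strongest reply is that SAP 4.12 is not the edit-check specification. Its ranges are introduced as examples, and SAP 1 says data are reviewed against the categories set by the CRF. Protocol 11.7.1 adds real-time checks at entry and provides that "Discrepancy reports will be generated accordingly and transferred to the study center for resolution by the investigator or his/her designee". If the CRF offers only 0 to 4, a 5 cannot be entered. If it stores 1 to 5, a 5 is legitimate and the range is right. A queried 0 goes back to the site, which can confirm it, and nothing requires a confirmed valid score to be removed.

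Most of this stands. It makes both the loss of a true 0 and the entry of a spurious 5 unlikely. It does not remove the contradiction. The CRF coding is not shown, so either the range is wrong or a recode is undocumented, and the text needs correcting in both cases. It is also fair that Table 14.2.1.20 is descriptive, and that the undefined percent change from a baseline of 0 comes from the 0-4 scale and the SAP 5.2 formula. Correcting 4.12 would not remove that.

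Two stronger readings are tempting:

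- **Material loss of power for the PGA test.** The documents give no proportion of patients scoring 0 at Week 12 and no reason to expect confirmed zeros to be excluded. Any power figure would rest on invented inputs.
- **Bias in favour of Ampion.** The PGA is also recorded at Screening ("The PGA should be completed by subjects at Screening"), and under SAP 4.4 "For analysis, the Baseline measure is the latest measure prior to initiation of treatment". If a baseline 0 were discarded, a worse Screening score might therefore take its place. That needs a patient with entry scores of at least 1.5 on WOMAC A and C who also reports doing very well, and then exclusion of that valid value. Nothing in the documents suggests this would occur often enough to matter.

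**Conclusion.** The range in SAP 4.12 is wrong as written against the protocol's PGA scale. That conclusion rests only on the two texts and needs no assumption about the data. If the database in fact stores 1 to 5, the defect becomes an unstated recode.

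The consequences are much less certain. PGA responder status is unaffected by a consistent choice of coding. The percent-change table is affected by that choice even if no value is ever excluded. Loss of PGA responses requires two further steps, exclusion of a genuine 0 and treatment of it as missing, and the site query process makes the first unlikely. The size of the effect is unknown and probably small; if no 0 is excluded, no responder result changes.

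**What to change.** In SAP 4.12, change the PGA range to zero to four. If the database stores PGA as 1 to 5, keep the range and state the recode from the protocol's codes instead. In either case, name one coding and use it for edit checks, percent change and imputation, settled before database lock.

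The cost is one line in the SAP. The design, sample size and hypotheses are unchanged.

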4.13 Testing/Validation Plan

All statistical analyses will be programmed using SAS[®] software version 9.3, or later. Testing and validation plans for all programs will be developed in accordance with contract statistical organization guidelines and will include independent programming of tables and analyses.

5. DEFINITIONS

5.1 Abbreviations

| Abbreviation | Definition |
|--------------|---|
| AE | Adverse Event |
| ANCOVA | Analysis of Covariance |
| ATC | Anatomical Therapeutic Chemical Classification System |

| | |
|---------------|--|
| CSR | Clinical Summary Report |
| ICH | International Conference on Harmonisation |
| MedDRA® | Medical Dictionary for Regulatory Activities |
| mL | Milliliter |
| NA | Not applicable |
| ng | Nanogram |
| NSAID | Non-steroidal anti-inflammatory drug |
| OA | Osteoarthritis |
| OAK | Osteoarthritis of the knee |
| OMERACT-OARSI | Outcome Measures in Rheumatology Clinical Trials and Osteoarthritis Research-Osteoarthritis Research Society International |
| PGA | Patient's global assessment of disease severity |
| PP | Per protocol population |
| SAE | Serious adverse event |
| SAS | Statistical Software from SAS Institute |
| SD | Standard deviation |
| SEM | Standard error of the mean |
| TEAE | Treatment-emergent adverse event |
| WO | Washout |
| WOMAC | Western Ontario and McMaster Universities Arthritis Index |

5.2 Definitions

Adverse Event (AE)

An adverse event (AE) is defined as any undesired medical occurrence in a patient or clinical investigation patient receiving a pharmaceutical product and which does not necessarily have a causal relationship with this treatment. An AE can therefore be any unfavorable sign and unintended sign (including an abnormal laboratory finding comparing pre-treatment to post-treatment), symptom, or disease temporarily associated with the use of a study drug, whether or not related to the study drug.

AEs will be graded for severity using the following categories. Missing grade will be assigned a grade of 3 (severe) in tabulations.

Grade 1 (MILD): The symptom is barely noticeable to the study patient and does not influence performance or functioning. Concomitant medication is not ordinarily indicated for relief of mild AEs.

Grade 2 (MODERATE): The symptom is of sufficient severity to make the study patient uncomfortable and to influence performance of daily activities. Concomitant medication may be indicated for relief of moderate AEs.

Grade 3 (SEVERE): The symptom causes severe discomfort, sometimes of such severity that the study patient cannot continue in the study. Daily activities are significantly impaired or prevented by the symptom. Concomitant medication may be indicated for relief of severe AEs.

Relationship to study drug will be coded using the following categories. Missing relatedness will be assigned to “related” in tabulations.

Unrelated: The adverse event is unlikely to have been caused by study drug.

Possibly related: It is unclear whether the adverse event may have been caused by study drug.

Related: The adverse event is likely to have been caused by study drug.

Serious Adverse Event:

A serious adverse event (SAE) is defined as an adverse event that

- Results in death
- Is life-threatening (patient is at immediate risk of death from the event as it occurred)
- Requires in-patient hospitalization (formal admission to a hospital for medical reasons) or prolongation of existing hospitalization
- Results in persistent or significant disability/incapacity
- Results in a congenital anomaly/birth defect

Treatment-Emergent AE:

A Treatment-Emergent AE (TEAE) is any AE that begins or increases in severity after the initial dose of study drug.

Age

Subject’s age is defined as its integer value in years at enrollment.

Baseline

For any variable, unless otherwise defined, Baseline is the last assessment taken prior to the first study drug administration.

Change from Baseline:

The arithmetic difference between a post-Baseline value and the Baseline value:

Change from Baseline = (Post-Baseline Value – Baseline Value)

Percentage Change from Baseline = [(Post-baseline Value – Baseline Value) / Baseline Value] x 100

End of Study

End of study is at Visit 9 (day 84 ± 7 days), unless terminated early.

Enrollment date

Enrollment date is the same as the randomization date and is designated Day 0.

Study drug

Study drug in this study is Ampion or saline.

Randomization date

Randomization date is the day the subject is assigned a randomization number on study Day 0.

Study Day 0

Day 0 is defined as the first day that study drug is administered to the subject.

Study Day

Day of treatment: study day = (visit date - date of Study Day 0)

6. CHANGES FROM PROTOCOL-SPECIFIED ANALYSES

Modifications to the planned statistical analyses should be minimized. Nonetheless, the data obtained from the study may indicate that the planned analyses are inappropriate, that additional analyses need to be performed, or that the design of the study needs to be modified, due to factors such as the distribution of the data or imbalance in important covariates. The study report will provide a detailed explanation for any deviations from the planned analyses.

7. LIST OF PLANNED TABLES, FIGURES, AND LISTINGS

Tables are categorized and numbered in accordance with ICH E3 guidelines. Each table, figure and listing is presented by treatment arm. All efficacy tables will be provided both for ITT and PP. Accountability tables will also include an overall column. Listings will be sorted by treatment, subject ID, and by visit, if multiple visits exist. These will be provided in a separate document.

| Number | Title |
|----------------------------|--|
| 14.1 Accountability | |
| 14.1.1 | Accountability (Analysis Population: All Enrolled) |
| 14.1.2 | Enrollment by Site (Analysis Population: All Enrolled) |
| 14.1.3 | Analysis Populations (include ITT, safety, PP, and reasons for PP exclusion) |
| 14.1.4 | Subject Disposition (all screened) |
| 14.1.5 | Major Protocol Deviations (Analysis Population: All Enrolled) |
| 14.1.6.1 | Demographics and Baseline Characteristics (Analysis Population: ITT) |
| 14.1.6.2 | Demographics and Baseline Characteristics (Analysis Population: PP) |
| 14.2 Efficacy | |

| Number | Title |
|--------------------|--|
| 14.2.1.1 | Summary of OMERACT-OARSI Percent Responder Status (Analysis Population: ITT) |
| 14.2.1.2 | Summary of OMERACT-OARSI “Controlled” Responders (WOMAC A and C) |
| 14.2.1.3 | Summary of Responders Demonstrating a 20% Improvement and 0.5 Shift in PGA |
| 14.2.1.4 | Summary of OMERACT-OARSI “Controlled” Responders (WOMAC A and C) Compared to Historic Saline |
| 14.2.1.5 | Summary of OMERACT-OARSI Percent Responder Status for a 50% Threshold |
| 14.2.1.6 | Summary of Patients Responding to 50% Improvement in Pain and 1.0 Absolute Change |
| 14.2.1.7 | Summary of Patients Responding to a 50% Improvement in Function and 1.0 Absolute Change |
| 14.2.1.8 | Summary of Patients Responding to a 20% Improvement in Pain and 0.5 Absolute Change |
| 14.2.1.9 | Summary of Patients responding to a 20% Improvement in Function and 0.5 Absolute Change |
| 14.2.1.10 | Summary of Patients responding to a 20% Improvement in PGA and 0.5 Absolute Change |
| 14.2.1.11 | Summary of WOMAC A mean change |
| 14.2.1.12 | Summary of WOMAC A percent change |
| 14.2.1.13 | Summary of WOMAC B mean change |
| 14.2.1.14 | Summary of WOMAC B percent change |
| 14.2.1.15 | Summary of WOMAC C mean change |
| 14.2.1.16 | Summary of WOMAC C percent change |
| 14.2.1.17 | Summary of WOMAC A and C mean change |
| 14.2.1.18 | Summary of WOMAC A and C percent change |
| 14.2.1.19 | Summary of PGA mean change |
| 14.2.1.20 | Summary of PGA percent change |
| 14.2.1.21 | Summary of WOMAC mean change |
| 14.2.1.22 | Summary of WOMAC percent change |
| 14.3 Safety | |
| 14.3.1 | Overall Summary of TEAEs (Analysis Population: Safety) |
| 14.3.2 | Incidence of TEAEs by System Organ Class and Preferred Term (Analysis Population: Safety) |
| 14.3.3 | Incidence of Treatment Emergent Related AEs by System Organ Class and Preferred Term |
| 14.3.4 | Incidence of Treatment Emergent Serious AEs by System Organ Class and Preferred Term |
| 14.3.5 | Incidence of TEAEs by Preferred Term in Descending Order of Frequency |
| 14.3.6 | Incidence of Treatment Emergent Related AEs by Preferred Term in Descending Order of Frequency |
| 14.3.7 | Summary of Lab Value and Change from Baseline |
| 14.3.8 | Shifts in Reference Range |
| 14.3.9.1 | Summary of Vital Signs and Change from Baseline: Pulse (bpm) |
| 14.3.9.2 | Summary of Vital Signs and Change from Baseline: Temperature (°F) |
| 14.3.9.3 | Summary of Vital Signs and Change from Baseline: Systolic Blood Pressure (mmHG) |
| 14.3.9.4 | Summary of Vital Signs and Change from Baseline: Diastolic Blood Pressure (mmHG) |
| 14.3.10.1 | Concomitant Medication Use by ATC Level 1 and WHO Preferred Term |
| 14.3.10.2 | Medication started on study by ATC Level 1 and WHO Preferred Term |

| Number | Title |
|---------------------|---|
| 14.3.10.3 | Concomitant Medication Use by WHO Preferred Term in Descending Order of Use |
| 14.3.10.4 | Concomitant Medication Use by WHO Preferred Term in Descending Order of Use for Historic Control |
| 14.3.10.5 | Medication Started on Study by WHO Preferred Term in Descending Order of Use |
| 16- Listings | |
| 16.1 | Randomization List |
| 16.2 | Inclusion/Exclusion Criteria |
| 16.3 | Protocol Deviations |
| 16.4 | Early Terminations (Include date of ET and reason for ET) |
| 16.5 | Exclusions from PP |
| 16.6 | Demographics and Baseline Characteristics |
| 16.7 | Demographics and Baseline Characteristics for Historic Control |
| 16.8 | Medical History |
| 16.9 | Concomitant Medications |
| 16.10 | WOMAC/PGA/OMERACT OARSI Responder Status |
| 16.11 | Analgesic Used within 24 hours of visit |
| 16.12 | Adverse Events |
| 16.13 | Serious Adverse Events |
| 16.14 | Laboratory Values |
| 16.15 | Physical Exam (weight (lbs), Height, any abnormality (if listed)) and Vital Signs (BP, Temp, Pulse) |
| 16.16 | X-ray Data (and abnormalities, if listed) |
| 16.17 | OMERACT-OARSI Responder Status (WOMAC A, C, and PGA) |
| 10.3 Figures | |
| 10.3.1 | OMERACT-OARSI Responder Over 12 Weeks |
| 10.3.2 | WOMAC A Pain Scale Over 12 Weeks |
| 10.3.3 | WOMAC C Function Over 12 Weeks |
| 10.3.4 | PGA Over 12 Weeks |
| 10.3.5 | Rescue Med Use Over 12 Weeks |
| | |

